### 6.4.1 Analysis variables

The analysis variables consist of baseline participant characteristics, safety, and immunogenicity for primary- and secondary-objective analyses.

### 6.4.2 Baseline comparability

Treatment arms will be compared for baseline participant characteristics using descriptive statistics.

### 6.4.3 Safety/tolerability analysis

Since enrollment is concurrent with receiving the first vaccination, all participants will have received at least 1 vaccination and therefore will provide some safety data.

#### 6.4.3.1 Reactogenicity

The number and percentage of participants experiencing each type of reactogenicity sign or symptom will be tabulated by severity and treatment arm and the percentages displayed graphically by arm. For a given sign or symptom, each participant's reactogenicity will be counted once under the maximum severity for all injection visits. In addition, to the individual types of events, the maximum severity of local pain or

tenderness, induration or erythema, and of systemic symptoms will be calculated. Kruskal-Wallis tests will be used to test for differences in severity between arms.

#### 6.4.3.2 AEs and SAEs

AEs will be summarized using MedDRA System Organ Class and preferred terms. Tables will show by treatment arm the number and percentage of participants experiencing an AE within a System Organ Class or within preferred term category by severity or by relationship to study product. For the calculations in these tables, a participant with multiple AEs within a category will be counted once under the maximum severity or the strongest recorded causal relationship to study product. Formal statistical testing comparing arms is not planned since interpretation of differences must rely heavily upon clinical judgment.

A listing of SAEs reported to the DAIDS Regulatory Support Center (RSC) Safety Office will provide details of the events including severity, relationship to study product, time between onset and last vaccination, and number of vaccinations received.

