### **Duration per participant**

**Part A:** 18 months of scheduled clinic visits (main study) followed by a health contact at month 24

**Part B:** 22 months of scheduled clinic visits (main study) followed by a health contact at month 28

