## 9.5 Contact at 6 months after last scheduled visit

CRS staff will contact study participants at 6 months after the last scheduled visit to collect the information listed below. This contact may be accomplished by phone, text message, or email. If indicated, the participant may be asked to come in for a clinical assessment which may also include referrals for AESI assessment. AESIs are described further in Appendix M.

- Confirmation of vital status; if deceased, attempt to learn cause and date of death
- If participant is alive, record the participant's responses to the following:
  - Assessment of new or unresolved AEs/intercurrent illnesses:
    - Life threatening adverse experiences;
    - Persistent or significant disability/incapacity;
    - Hospitalizations and reasons;
    - Other important medical events that may jeopardize the participant or may require intervention to prevent 1 of the other outcomes listed above;
    - New chronic conditions requiring more than 30 days of medical intervention or medication;
    - AESI (Section 11.2.2. A sample list of AESI is provided in Appendix M);
    - New diagnosis of HIV infection; and
    - Pregnancies and outcomes, including congenital anomalies/birth defects.

All such events will be recorded and adverse events will be assessed for relationship to study products.

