### **11.2.3 Expedited reporting of adverse events to DAIDS**

Requirements, definitions and methods for expedited reporting of AEs are outlined in Version 2.0 (January 2010) of the *Manual for Expedited Reporting of Adverse Events* to DAIDS (DAIDS EAE Manual), which is available on the RSC website at <http://rsc.tech-res.com/safetyandpharmacovigilance/>. The SAE Reporting Category will be used for this study.

The internet-based DAIDS Adverse Experience Reporting System (DAERS) must be used for expedited AE reporting to DAIDS. In the event of system outages or technical difficulties, expedited AE reports may be submitted via the DAIDS EAE Form. For

questions about DAERS, please contact [[contact]](mailto:[contact]) or from within the DAERS application itself.

Sites where DAERS has not been implemented will submit expedited AE reports by documenting the information on the current DAIDS EAE Form. This form is available on the RSC website: <http://rsc.tech-res.com/safetyandpharmacovigilance/>. For questions about expedited AE reporting, please contact the RSC ([[contact]](mailto:[contact])).

The study products for which expedited reporting are required are

- CH505TF HIV gp120 with GLA-SE or placebo
- CH505w53 HIV gp120 with GLA-SE or placebo
- CH505w78 HIV gp120 with GLA-SE or placebo
- CH505w100 HIV gp120 with GLA-SE or placebo
- DNA Mosaic-Tre *env* or placebo

While the participant is in the main study reporting period (See Section 3), the SAE Reporting Category will be used.

After the protocol-defined AE reporting period for the study, unless otherwise noted, only Suspected, Unexpected Serious Adverse Reactions as defined in Version 2.0 of the DAIDS EAE Manual must be reported to DAIDS, if the study staff become aware of the events.

The NIAID/DAIDS will report all unexpected SAEs related to the study products observed in this clinical trial to the FDA in accordance with 21 CFR 312.32 (IND Safety Reports). However, because safety is a primary study endpoint, the Sponsor Medical Officer will not routinely be unblinded to study treatment assignment when there is an assessment of relatedness of the SAE with the study product(s); and the safety report will be sent to the FDA based on the blinded attribution assessment.

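### The only SAE listing is drawn from reports to the DAIDS RSC, so a serious event first recorded at the month 24/28 contact and judged unrelated or expected need not appear in it

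*Combined protocol and SAP*

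**What the plan says.** SAEs are named in primary endpoint 1 for both parts (Sections 5.1 and 5.4). Section 6.4.3.2 plans two kinds of AE output:

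- By-arm tables: "AEs will be summarized using MedDRA System Organ Class and preferred terms". They are broken down by severity or by relationship to study product.
- One SAE output: "A listing of SAEs reported to the DAIDS Regulatory Support Center (RSC) Safety Office will provide details of the events". Its columns include severity, relationship, time from last vaccination to onset, and number of vaccinations received.

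Section 11.2.3 decides what reaches the RSC. During the trial proper: "While the participant is in the main study reporting period (See Section 3), the SAE Reporting Category will be used". The duty narrows once an AE reporting period set by the protocol has ended. From then on, "only Suspected, Unexpected Serious Adverse Reactions as defined in Version 2.0 of the DAIDS EAE Manual must be reported to DAIDS", and this holds only where staff learn of the event.

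Section 3 uses the main-study label for the clinic-visit phase. Part A has "18 months of scheduled clinic visits (main study) followed by a health contact at month 24"; Part B has 22 months of visits and a contact at month 28.

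At that contact Section 9.5 asks about death, life-threatening events, disability, hospitalization, other important medical events, new chronic conditions and AESIs. It adds: "All such events will be recorded and adverse events will be assessed for relationship to study products". It does not say that these events go to the RSC.

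**The concern.** The listing takes its content from a regulatory reporting stream, not from the clinical database, and that stream narrows before follow-up ends. Up to the end of the main study, every SAE should be in it. After that, being listed is assured only for an event that someone has judged both related to product and unexpected.

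At stake is the completeness of the one SAE-specific display for a primary safety endpoint. A reader who finds no late entries could conclude that no serious event was recorded between the last clinic visit and the health contact, when the listing only shows that none had to be reported. These are first-in-human products, in a combination with the adjuvant that Section 4.4 says has not been given to humans before. Late serious events should therefore be visible whatever the causality call.

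**Working it through.** The documents state no figure to reproduce. The check sets the rules side by side and then sizes the window.

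**Which late events the rules put in the listing.** Take an event first found at the month 24/28 contact, and read the AE reporting period as ending with the main study.

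| Event at the contact | Recorded (9.5) | Must go to DAIDS (11.2.3) | Assured a place in the listing (6.4.3.2) |
|---|---|---|---|
| Serious, related, unexpected | Yes | Yes | Yes |
| Serious, related, expected | Yes | No | No |
| Serious, unrelated | Yes | No | No |
| Non-serious AESI | Yes | No | Not an SAE, so never |

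Section 11.2.3 allows exceptions where otherwise noted. Section 9.5 gives no instruction to forward contact events, so it does not supply one.

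**Where the unlisted events still appear.** Section 11.2.2 sends all AEs to the SDMC on CRFs, and the AE tables in Section 6.4.3.2 have no time cut-off. The second- and third-row events would therefore be counted by arm under their system organ class and preferred term, with severity or relationship. Those tables carry neither seriousness nor time since last vaccination. Severity grade is a different attribute from seriousness and does not replace it.

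**Whether month 18/22 is the right cut-off.** The narrower rule starts after an AE reporting period that is not defined anywhere in the documents.

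- Reading 1: the period equals the main study reporting period, which points to Section 3. The cut-off is then month 18 (Part A) or 22 (Part B). This is the natural reading.
- Reading 2: the period runs to month 24/28. The narrower rule would then not yet apply at the contact. But one sentence ties the SAE Reporting Category to the main study, while another in the same section applies it to this study without limit. The two sentences would give different answers for the last six months.

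Under either reading the passages have to be reconciled.

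**Size of the window** (visit days from Appendices I and J):

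- Part A: last clinic visit day 546, contact day 728, last vaccination day 364. 728 − 546 = 182 days. 182/728 = 25.0% of follow-up. 728 − 364 = 364 days after the last vaccination, and 182/364 = 50%.
- Part B: last clinic visit day 667, contact day 849, last vaccination day 485. 849 − 667 = 182 days. 182/849 = 21.4% of follow-up. 849 − 485 = 364, and 182/364 = 50%.
- Person-time, assuming full retention and counting the window as half a year: 116 × 0.5 = 58 vaccinee-years and 16 × 0.5 = 8 placebo-years.

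The documents give no SAE rate, so these figures cannot be turned into an expected number of unlisted events.

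**The case against.** The best reply is that nothing is lost. The events are recorded, go to the SDMC and enter the by-arm AE tables; an autoimmune diagnosis at month 24 would show under its own preferred term. The reporting duty is also a minimum. The listing covers what was reported, and sites may report more than they must. Serious reactions judged related and unexpected are still listed. All of this stands, and it limits the point to one listing. It does not remove the point, because no other planned output shows seriousness or timing.

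Several stronger readings are tempting and are not supported:

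- A reader might infer that late serious events vanish from the safety report. Sections 9.5, 11.2.2 and 6.4.3.2 together say otherwise.
- A reader might take month 18/22 as a stated cut-off. It is an inference from Section 3, because the AE reporting period is undefined.
- A reader might say that the contact, or the AESI list, exists to catch late immune-mediated harm. Section 9.5 states no such purpose, and AESIs are one item among several. Appendix M says only that AESIs include potential immune-mediated diseases. Table 4-8 names autoimmune disease as a theoretical risk without mentioning AESIs.
- A reader might count the absence of an AESI table as part of the same error. A non-serious AESI would not belong in an SAE listing at any time, so this is a separate reporting request.
- A reader might treat 58 and 8 person-years as the size of the loss. They measure follow-up in the window.

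It can also be said that Section 6.4 leaves some safety detail to the SAP. If table shells there define the SAE listing from the database, the gap closes, but the text available does not do so.

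**Conclusion.** The point holds in limited form. Followed as written, Section 6.4.3.2 can produce an SAE listing that is complete for the main study but selected by causality and expectedness judgments for the last 182 days of each participant's follow-up. Site staff are blinded (Section 6.3), so the selection is not driven by known assignment, but it still leaves out serious events judged unrelated. No estimate, test, sample size or stated figure changes.

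The conclusion rests on three assumptions: the AE reporting period ends with the main study, sites report no more than they must, and contact events are entered on CRFs as Section 11.2.2 describes. If the first is wrong, what remains is the undefined term and the two sentences in Section 11.2.3 that disagree. The change is worth making before the final analysis, because it concerns a primary safety endpoint and costs little.

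**What to change.** 1. In Section 6.4.3.2, base the listing on all SAEs recorded in the study database through the month 24/28 contact, whether or not they were reported to the RSC. Show arm, and flag each event as main study or health contact. Keep the columns already planned.
2. Define the AE reporting period, and reconcile Section 11.2.3 with Section 3 so that it is clear which rule covers the interval from the last clinic visit to the contact. This point takes no position on what the expedited reporting rule should be; those rules stay unchanged.
3. Optionally, add a by-arm AESI listing with time since last vaccination. This would help the reader but is not part of the error.

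The cost is wording, plus carrying a seriousness flag and an onset date from the health-contact form into the analysis data. That form is not in the documents, so whether it already holds both fields has to be checked. If it does not, they must be added. No new visit or procedure is needed.

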#### 6.4.3.3 Local laboratory values

Box plots of local laboratory values will be generated for baseline values and for values measured during the course of the study by treatment arm and visit. Each box plot will show the first quartile, the median, and the third quartile. Outliers (values outside the box plot) will also be plotted. If appropriate, horizontal lines representing boundaries for abnormal values will be plotted.

For each local laboratory measure, summary statistics will be presented by treatment arm and timepoint, as well as changes from baseline for postenrollment values. In addition, the number (percentage) of participants with local laboratory values recorded as meeting Grade 1 AE criteria or above as specified in the Division of AIDS Table for Grading the Severity of Adult and Pediatric Adverse Events (Section 9.10) will be tabulated by treatment arm for each postvaccination timepoint. Reportable clinical laboratory abnormalities without an associated clinical diagnosis will also be included in the tabulation of AEs described above.

#### 6.4.3.4 Reasons for vaccination discontinuation and early study termination

The number and percentage of participants who discontinue vaccination and who terminate the study early will be tabulated by reason and treatment arm.

### 6.4.4 Immunogenicity analysis

#### 6.4.4.1 General approach

Discrete categorical assay endpoints (eg, response rates) will be analyzed by tabulating the frequency of positive response for each assay by antigen and treatment arm at each timepoint for which an assessment is performed. Crude response rates will be presented with their corresponding 95% confidence interval estimates calculated using the score test method [59]. Because of the small numbers of control participants, no adjustment will be made to the vaccine arm estimates for the false positive rates in the control arms. To address the aims of Part B, Barnard or Fisher's exact tests, as specified in the SAP, will be used to compare the response rates of any 2 vaccine arms and of pooled groups as described in Section 4.1.2, with a significant difference declared if the 2-sided p-value is

$\leq 0.05$ . In general, Barnard's is preferred since under most circumstances it is more powerful than Fisher's [60].

In addition to response rate estimates for each timepoint, the probability of observing at least 1 positive response by a given timepoint and the probability of observing more than 1 positive response by a given timepoint will be estimated, with corresponding confidence intervals, for each vaccine arm using maximum likelihood-based methods [61].

For quantitative assay data (eg, magnitudes and magnitude-breadth AUCs from the neutralizing antibody multiplex assay or percentage of positive cells from the ICS assay), graphical and tabular summaries of the distributions by antigen, treatment arm, and timepoint will be made. For all primary and secondary immunogenicity endpoints, box plots and plots of estimated reverse cumulative distribution curves will be used for graphical display of all of the study arms. Typically the results will be shown for each vaccine arm and for the set of control arms pooled into 1 group.

To test for differences among the vaccine arms in Part A and separately in Part B, first a Kruskal-Wallis rank test or an F-test (depending on the normality assumption) will be used to test for overall differences. Secondly, if the overall test is significant at the 2-sided 0.05 level, then individual tests comparing the 2 adjacent pairs of vaccine arms (Part A) and all 6 pairs of 4 vaccine arms (Part B) will be done unless pre-specified. If rank-based tests are used then the tests will be inverted to construct Hodges-Lehmann point estimates and 2-sided  $(1-0.05/k) \times 100\%$  CIs about the differences in location centers of the  $k = 2$  (Part A) or  $k = 6$  (Part B) pair-wise comparisons of vaccine arms. If actual-value tests are used then the Dunnett's procedure will be used to construct simultaneous confidence intervals about the pairs of mean differences for the many-to-one comparisons [62] when multiple vaccine arms are each compared with 1 common control arm. When all pair-wise comparisons between the multiple vaccine arms are of interest, the Tukey procedure [63] will be used. If only specific comparisons between pairs of the multiple vaccine arms are of interest, the Holm-Bonferroni procedure will be used. An appropriate data transformation (eg,  $\log_{10}$  transformation) may be applied to better satisfy assumptions of symmetry and homoscedasticity (constant variance). Significance of the differences between pairs will be evaluated using 2 procedures, first based on whether the simultaneous 95% CIs exclude zero and secondly based on whether the nominal (unadjusted) 95% CIs exclude zero.

Some immunologic assays have underlying continuous or count-type readout that are dichotomized into responder/nonresponder categories (eg, nAb multiplex assay positivity). If treatment arm differences for these assays are best summarized by a mixture model, then Lachenbruch's test statistic [64] or an alternative two-part test [65] (as defined in the SAP) will be used to evaluate the composite null hypothesis of equal response rates in the 2 arms and equal response distributions. Lachenbruch's test statistic equals the square of a binomial Z-statistic for comparing the response rates plus the square of a Wilcoxon statistic for comparing the response distributions in the subgroup of responders. A permutation procedure is used to obtain a 2-sided p-value. For estimation, differences in response rates between arms will be estimated using the methods described above, and in the subgroup of positive responders, differences in location parameters between arms will be estimated using the methods described above.

Based upon previous HVTN trials, missing 10% of immunogenicity results for a specific assay is common due to study participants terminating from the study early, problems in

shipping specimens, or low cell viability of processed peripheral blood mononuclear cells (PBMCs). To achieve unbiased statistical estimation and inferences with standard methods applied in a complete-case manner (only including participants with observed data in the analysis), missing data need to be missing completely at random (MCAR). Following the most commonly used definition, MCAR assumes that the probability of an observation being missing does not depend on any participant characteristics (observed or unobserved). When missing data are minimal (specifically if no more than 20% of participants are missing any values), then standard complete-case methods will be used, because violations of the MCAR assumption will have little impact on the estimates and hypothesis tests.

If a substantial amount of immunogenicity data are missing for an endpoint (at least 1 value missing from more than 20% of participants), then using the methods that require the MCAR assumption may give misleading results. In this situation, analyses of the immunogenicity endpoints at a specific timepoint will be performed using parametric generalized linear models fit by maximum likelihood. These methods provide unbiased estimation and inferences under the parametric modeling assumptions and the assumption that the missing data are missing at random (MAR). MAR assumes that the probability of an observation being missing may depend upon the observed responses and upon observed covariates, but not upon any unobserved factors. Generalized linear models for response rates will use a binomial error distribution and for quantitative endpoints, a normal error distribution. For assessing repeated immunogenicity measurement, linear mixed effects models will be used. If the immunological outcomes are left- and/or right-censored, then the linear mixed effects models of Hughes [66] will be used, because they accommodate the censoring. In addition, secondary analyses of repeated immunogenicity measurements may be done using weighted GEE [67] methods, which are valid under MAR. All of the models described above in this paragraph will include as covariates all available baseline predictors of the missing outcomes.

Some “resource-intensive” immunogenicity endpoints are only measured in subset of participants, eg, immunogenicity endpoints based on mucosal samples. For such endpoints, exploratory analyses will be conducted to assess the correlation of participant characteristics measured in (nearly) all subjects with the resource-intensive endpoints. For example, if the same assay is performed on blood and mucosal samples, then a scatterplot and Spearman rank correlation coefficient ( $r$ ) will be used to assess the correlation of responses. If at least moderate correlations exist (eg,  $r \geq 0.3$ ), then the semiparametric efficient analysis method of Rotnitzky and Robins [68] will be used (described in Gilbert, Sato et al. for application to vaccine studies [69]) to estimate the mean of the resource-intensive endpoint for each group and to compare means between groups.

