binding Ab response to a panel of gp120 proteins and of the neutralization of tier 1 and tier 2 panels of HIV-1 viruses. Each analysis will be conducted separately for each of 2 pooled comparisons (additive vs sequential, pooling over groups with and without mosaic DNA: Groups 5 and 6 combined vs Groups 7 and 8 combined; effect of mosaic DNA, pooling over groups receiving additive and sequential proteins: Groups 5 and 7 combined vs Groups 6 and 8 combined), and for each of 6 pairwise comparisons among these groups using a two- sided Wilcoxon rank sum test with 5% type-I error rate per pooled comparison and a 5%/6 type-I error rate per pairwise comparison. The sample size of 20 vaccinees per group will give 80% power to detect a true difference of 1.63 standard deviations (SDs) between the mean non-zero responses and 90% power to detect a true difference of 1.81 SDs for the pairwise comparisons. Using the mean and SD values from the HVTN 088 trial, the difference of 1.63 SDs translates to a difference of 0.637 units of  $\log_{10}$  binding magnitude; if 1 of the comparison groups has the same mean as was seen among non-negative values among vaccine recipients in the HVTN 088 trial (4.06 units), then after incorporating the expected 6% zero-valued (negative responder) measures, this corresponds to observing an increase or decrease in the overall mean from 3.609 in group 1 to 4.175 in group 2. The sample size of 40 vaccinees per pooled group will give 80% power to detect a true difference of 0.80 standard deviations (SDs) between the mean non-zero responses and 90% power to detect a true difference of 0.90 SDs (these 2 are each conducted at a 5% alpha level). Using the mean and SD values from the HVTN 088 trial, the difference of 0.80 SDs translates to a difference of 0.313 units of  $\log_{10}$  binding magnitude; if 1 of the comparison groups has the same mean as was seen among non-negative values among vaccine recipients in the HVTN 088 trial (4.06 units), then after incorporating the expected 6% zero-valued (negative responder) measures, this corresponds to observing an increase or decrease in the overall mean from 3.722 in group 1 to 4.007 in group 2. These calculations assume a 10% loss-to-follow-up rate and the (94%) response rate observed in the HVTN 088 vaccine recipients. The same approach will be used to test superiority of the magnitude of the IgG binding Ab response to each individual gp120 antigen in the binding panel.

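### Pairwise significance is judged by both adjusted and unadjusted intervals with no deciding rule; in Part B the unadjusted rule alone can reach about 12% family-wise error

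*Combined protocol and SAP*

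**What the plan says.** Section 6.4.4.1 starts with an overall Kruskal-Wallis or F-test among the vaccine arms of each part. Pairs follow "if the overall test is significant at the 2-sided 0.05 level". In Part A these are the two adjacent dose pairs; in Part B, "all 6 pairs of 4 vaccine arms (Part B) will be done unless pre-specified".

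The adjusted intervals depend on the method. Rank-based tests use Hodges-Lehmann intervals at level 1 − 0.05/k, with k = 2 or 6. For actual-value tests, "When all pair-wise comparisons between the multiple vaccine arms are of interest, the Tukey procedure [63] will be used", and Holm-Bonferroni is named where only specific pairs are of interest.

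The section then says: "Significance of the differences between pairs will be evaluated using 2 procedures". These are "first based on whether the simultaneous 95% CIs exclude zero" and "secondly based on whether the nominal (unadjusted) 95% CIs exclude zero". No precedence is given.

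Section 6.1.2 sizes Part A at 5%/2 per pair and Part B at "5% type-I error rate per pooled comparison and a 5%/6 type-I error rate per pairwise comparison".

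Section 6.4.4.3 compares neutralization AUC-MB among regimens that pass the tier 2 screen. After a significant F-test it forms intervals that it calls simultaneous, but it builds them from the 97.5th percentile of a t-distribution and declares a difference by Fisher's least significant difference (LSD) rule.

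**The concern.** Both intervals in Section 6.4.4.1 are named as ways to judge significance; the nominal one is not labelled descriptive. The same pair can therefore be significant by one rule and not by the other in one report, with nothing to settle it.

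With three arms, a significant overall test followed by unadjusted pairs keeps family-wise error near 5%. With four arms it does not. If one regimen stands out, the overall test nearly always passes, and three unadjusted 5% tests remain among the arms that are truly equal.

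These comparisons carry weight. Comparing sequential with additive immunization, with and without DNA, is primary objective 2 of Part B (Section 5.4). Section 4.5.1 says the simpler sequential schedule would be preferred if it proves as effective as the additive one.

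**Working it through.** **Inputs (Section 6.1.2).** 20 per Part B arm and 12 per Part A arm; 10% missing; 94% non-zero responses; non-zero log10 response with mean 4.06 and SD 0.391; Part B pairwise alpha 0.05/6 = 0.00833, so 6 × 0.00833 = 0.05.

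**Step 1: reproduce the plan's power.** Evaluable per Part B arm: 0.9 × 20 = 18. The stated overall means imply 2 zeros in 18: 16/18 × 4.06 = 3.609 and 16/18 × (4.06 + 0.637) = 4.175, both as printed. Simulated two-sided Wilcoxon tests at 0.05/6 (40,000 runs) give:
- 1.63 SD: 79.6–80.0% (stated 80%)
- 1.81 SD: 89.9–90.0% (stated 90%)

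So the trial was sized on the adjusted rule. At a nominal 5%, power at 1.63 SD would be about 97%.

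**Step 2: the maximum for the nominal rule.** Once the overall test is sure to pass, the chance of a false claim among m equal arms is the chance that their range exceeds the LSD limit:

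P(Q(m, df) > √2 × t(0.975, df)), where Q is the studentized range.

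With 18 per arm, df = 4 × 18 − 4 = 68, t = 1.995 and the limit is 1.4142 × 1.9955 = 2.822.
- m = 3 (one arm apart): 12.1%
- m = 4 (all equal, no overall test): 20.0%
- two separated equal pairs, treated as independent: 1 − 0.95² = 9.75%

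With 20 per arm (df = 76) the first two become 12.1% and 20.0%.

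**Step 3: simulate the full sequence.** The F route used 200,000 runs at 18 and 20 per arm. The rank route used 20,000 runs at 18 per arm, with no zeros or 6% zeros (the 0.5 SD row with zeros only).

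| True configuration, Part B | F-test, then nominal t | Kruskal-Wallis, then nominal Wilcoxon | Kruskal-Wallis, then Wilcoxon at 0.05/6 |
|---|---|---|---|
| All four equal | 5.0–5.1% | 4.5–4.7% | 3.0–3.2% |
| Three equal, one 0.5 SD away | 8.4–8.7% | 6.7% | 1.9% |
| Three equal, one 1 SD away | 12.0% | 10.8–11.0% | 1.8% |
| Three equal, one 1.63 SD away | 12.0–12.2% | 11.7–11.8% | 2.0–2.1% |
| Three equal, one 3 SD away | 12.0–12.1% | 11.4–11.6% | 1.9–2.0% |
| Two equal pairs, 3 SD apart | 9.7% | 9.2–9.4% | 1.3–1.4% |

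Tukey intervals give at most about 5.0% (all arms equal, no overall test) and 2.8% with one arm at least 1 SD away.

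**Step 4: how often the rules disagree.** On the rank route, at least one pair is significant at 5% but not at 0.05/6 in about 47% of trials with one arm shifted 1 SD, and about 30% with one arm shifted 1.63 SD.

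**Step 5: Part A.** With 0.9 × 12 = 10.8, taken as 11 per arm, nominal Wilcoxon tests on the two adjacent pairs after the overall test give 3.7% (all equal) and 4.6% (third arm 1.81 SD away). Without the overall test and with all arms equal they give 8.4%, or 9.2% in large samples.

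**The case against.** The adjusted rule is already in the plan and is listed first; 5%/6 is the k = 6 rule. The nominal interval could be read as planned dual reporting, since Section 6.4.4.3 says nominal intervals will also be reported. Both results would be labelled. This is a phase 1 trial described as the first of an iterative series, and Section 6.4 waives adjustment across endpoints.

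Much of this stands, and it limits the severity. A reader might infer that the plan runs Part B at 12% error. The documents do not support that: nowhere does Section 6.4.4.1 let the nominal interval decide alone, and 12% is that rule's worst case. Part B is also a 2×2 layout. A single main effect leaves two equal pairs, about 9%; if both factors act equally and additively, one null pair remains, about 5%.

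Three parts do not stand:
- Listing a rule first does not make it decide.
- The Section 6.4 waiver covers multiple endpoints, not pairs of arms within one endpoint, where the plan does adjust.
- Part A cannot be exempted on the ground that the overall test protects it. Section 6.1.2 names its pairs in advance, so the exception for pre-specified pairs may remove that test, and the missing deciding rule applies there as well.

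**Conclusion.** The point holds as an unresolved rule that departs from the plan's own error rate. Section 6.4.4.1 evaluates significance two ways without precedence, and only one way matches the 5%/2 and 5%/6 of Section 6.1.2.

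For Part B, the nominal rule taken alone has a conditional maximum of about 12%, falling to about 9% with two equal pairs and about 5% with all arms equal. If the overall test is skipped, it is about 20% with all arms equal. The adjusted rank rule after the overall test stays at about 3% or below.

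Section 6.4.4.3 is the clearer case, because there the unadjusted t interval is the sole deciding rule for AUC-MB. Its error is likewise up to about 12% if four regimens advance. With three or fewer, the F-test keeps it near 5%.

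The figures assume equal variances, normal non-zero responses and 18 to 20 evaluable per arm. They do not cover multiplicity across endpoints or visits, or the two pooled contrasts.

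**What to change.** In Section 6.4.4.1, state that for quantitative endpoints in both parts a pair is declared different only if the multiplicity-adjusted result is significant: rank-based intervals with k = 2 or k = 6, Tukey, or Holm-Bonferroni, whichever applies. State that nominal 95% intervals are reported as descriptive. Say whether the pairs named in Section 6.1.2 count as pre-specified, so that it is clear whether the overall test applies. Limiting the sentence to quantitative endpoints leaves untouched the separate p ≤ 0.05 rule for response rates in the same section.

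In Section 6.4.4.3, replace the unadjusted t quantile with a Tukey or other adjusted quantile, or stop calling the intervals simultaneous and using them to declare differences.

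The cost is a few sentences, with no change to sample size, data or conduct. Fewer pairs will be called significant: power at 1.63 SD is the stated 80%, not the roughly 97% of the nominal test.
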